Dilatation (cm)	1	1-2	3-4	>4
Length of cervix (cm)	>4	2-4	1-2	<1
Station	-3	-2	-1	0
Consistency	Firm	Average	Soft	-

Position	Posterior	Mid/Anterior	-	-
----------	-----------	--------------	---	---

SELECTION AND WITHDRAWAL OF SUBJECTS

1. Sample population:
 - a. All pregnant women with one previous Caesarean section who are admitted to Sibug Hospital for IOL will be recruited in the study.
2. Inclusion criteria:
 - a. The inclusion criteria are age at least 18 years old, gestational age ≥ 37 weeks, singleton pregnancy, reassuring fetal status and modified Bishop score ≤ 6 .
3. Exclusion criteria:
 - a. Women with ruptured membranes, intrauterine death, polyhydramnios, severe fetal anomalies, multiple pregnancy.
 - b. Women with contraindications for IOL eg. placenta previa, suspected macrosomia, suspected cephalopelvic disproportion, non-cephalic presentation, and obstructive pelvic masses.
4. Sample size determination:
 - a. We had searched electronic databases including PubMed, Cochrane Library, Scopus, Ovid, JSTOR and Google Scholar. We found that there was no study comparing the two IOL methods, thus no prior information is available for sample size calculation.
 - b. Based on Julious SA (32), we will recruit 24 subjects (a sample size of 12 per group) first, then do an interim analysis and calculate the actual sample size required for a full RCT. The justifications for this interim sample size are based on rationale about feasibility, precision about the mean and variance, and regulatory considerations.
 - c. With α at 0.05 and power at 0.8, the final sample size will be calculated based on the study primary outcome of induction to delivery interval. As this outcome is a continuous data, we will use the following formula by Snedecor and Cochran 1989 to calculate the sample size (including 15% of dropout rate).

$$n = 1 + 2C \left(\frac{s}{d} \right)^2$$

s = standard deviation,

d = the difference to be detected, and

C = constant

5. Consent taking:

- a. Pregnant women with one previous Caesarean section who are indicated for IOL and eligible will be recruited in the study.
- b. Participation of the subjects is voluntary and will not affect medical services.
- c. Informed consent available in either English or Malay language (See Appendix 2) will be obtained prior to enrollment into the study.
- d. The consent will be taken by the principal investigator at time of admission in Sibu Hospital Labour Ward.

6. Subject withdrawal:

- a. Criteria:

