 - i. Subjects may withdraw voluntarily from study at any time upon their request.
 - ii. Subjects are inappropriately enrolled without fulfilling inclusion/exclusion criteria.
 - iii. Subjects develop spontaneous labour before IOL procedure is undertaken.
- b. Follow up process:
 - i. The withdrawn subjects will be managed according to local protocol under Department O&G, Sibu Hospital.
 - ii. The withdrawn subjects data will be destroyed as it will not be used for data analysis.
- c. The withdrawn subjects will be replaced with new subjects in order to meet the required sample size.

TREATMENT AND PROCEDURES

1. Treatment and medications that are permitted during the trial:
 - a. Amniotomy
 - b. Oxytocin augmentation when contractions are not optimised
 - c. Abdominal and vaginal examination to assess labour progress
 - d. Intrapartum continuous fetal heart rate monitoring
 - e. Fetal scalp sampling in the presence of non-reassuring fetal heart rate
 - f. Instrumental delivery or emergency Caesarean section if indicated

2. Both IOL methods of membrane sweeping and transcervical Foley catheter do not contain drug or medication. Thus, the risk of uterine rupture is similar to spontaneous labour in women with previous Caesarean delivery. If scar dehiscence is highly suspected during labour, standard management with recourse to emergency Caesarean section will be undertaken.

3. Treatment and medications that are not permitted during the trial:
 - a. Vaginal prostaglandin E2

ASSESSMENT OF EFFICACY

1. Primary outcome:
 - a. Overall induction to delivery interval.
2. Secondary outcomes:
 - a. Induction outcomes:
 - i. Improvement of modified Bishop score at interval of 24 hours and 48 hours after induction.
 - ii. Whether oxytocin augmentation is required.
 - b. Delivery outcomes:
 - i. Mode of delivery.
 - ii. Duration of oxytocin augmentation overall and in vaginal delivery group.
 - iii. Induction to vaginal delivery interval.

- iv. Amniotomy to vaginal delivery interval.
- v. Vaginal delivery rate within 24 hours of induction and between 24-48 hours of induction.
- c. Maternal outcomes:
 - vi. Uterine hyperstimulation (> 5 contractions per 10 minutes for at least 20 minutes or a contraction lasting at least 2 minutes with/without abnormal fetal heart rate).
 - vii. Uterine rupture.
 - viii. Post-partum haemorrhage (estimated blood loss \geq 500 ml).
 - ix. Maternal pyrexia (temperature >38.0 °C once, or 37.5 °C on two occasions 2 hours apart).

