 - x. Duration of hospitalisation.
- d. Neonatal outcomes:
 - i. APGAR score at 5 minutes.
 - ii. Cord pH.

ASSESSMENT OF SAFETY

1. No adverse events (AEs) will be expected during the course of study because there is no involvement of pharmacological drug or product. Both methods of membrane sweeping and transcervical Foley catheter do not contain drug or medication. Thus, the risk of uterine rupture is similar to spontaneous labour in women with previous Caesarean delivery. However, maternal discomfort and vaginal bleeding following membrane sweeping and unknown latex allergy following transcervical Foley catheter insertion may occur, and subjects will be informed of this risk in the informed consent.
2. All other invasive (amniotomy, fetal scalp sampling in the presence of non-reassuring fetal heart rate, instrumental delivery or emergency Caesarean section if indicated) and non-invasive procedures (maternal vital signs observation and intrapartum continuous fetal heart rate monitoring) and evaluations (abdominal and vaginal examination to assess labour progress) included in this protocol are considered to be standard of care in evaluation and management of women with one previous Caesarean delivery undergoing IOL and would have been performed as part of routine practice.

3. Report of adverse events eg. SAEs, SUSARs.
 - a. When adverse event of any type occurs, local SAE/SUSAR report will be created by principal investigator and notified via SAE Platform on NMRR website.
 - b. Subjects who experience SAE/SUSAR will be followed up by principal investigator and a follow up report will be submitted.
 - c. For “Non-life threatening SUSARs” eg. latex allergy associated with Foley catheter insertion, vasovagal attack following membrane sweeping, and cervical tear, initial report is to be submitted within 15 calendar days followed by a follow up report.
 - d. For “Life threatening SUSARs” eg. uterine rupture and maternal sepsis, initial report is to be submitted within 7 calendar days followed by a follow up report within the next 8 calendar days.

4. Process and duration of follow-up of adverse events
 - a. Latex allergy associated with Foley catheter insertion
 - i. Foley catheter will be removed immediately.
 - ii. Steroids and anti-histamine will be administered as rescue medication.
 - iii. Closed monitoring of vital signs and oxygen saturation for 24 hours.
 - b. Vasovagal attack following membrane sweeping

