 - i. No further membrane sweeping will be performed.
 - ii. Affected subject will be withdrawn from the study.
 - iii. No rescue medication is needed as condition is self-limiting.
 - iv. Closed monitoring of vital signs and oxygen saturation for 24 hours.
 - c. Cervical tear
 - i. Examination under anaesthesia will be performed immediately.
 - ii. Cervical repair will be performed.
 - iii. Subject will be followed up till 42 days post-delivery (completion of puerperal period).
 - d. Uterine rupture
 - i. Emergency laparotomy will be performed immediately.
 - ii. Depend on the severity of uterine rupture, uterine repair or hysterectomy may be warranted.

- iii. Subject will be followed up till 42 days post-delivery (completion of puerperal period).
 - e. Maternal sepsis
 - i. Blood culture and high vaginal swab for culture will be taken.
 - ii. Broad spectrum antibiotics will be started as rescue medication.
 - iii. Unstable subjects will be nursed in intensive care unit.
 - iv. Subject will be followed up till 42 days post-delivery (completion of puerperal period).
5. Compensation of adverse events
- a. In the event of a bodily injury or illness directly resulting from the membrane sweeping or transcervical Foley catheter insertion, the department will pay for reasonable and necessary treatment.
 - b. The department is not responsible for medical expenses due to pre-existing medical conditions, any underlying diseases, any ongoing treatment process, subjects' negligence or willful misconduct, the negligence or willful misconduct of the investigators or the study site or any third parties.

STATISTICS

1. All results will be analysed using the Statistical Package for Social Sciences for Windows (SPSS for Windows).
2. Normality of numerical data (Bishop score, induction to delivery interval, induction to vaginal delivery interval, amniotomy to vaginal delivery interval, duration of oxytocin augmentation, duration of hospitalisation, APGAR score at 5 minutes, cord pH, neonatal birth weight) will be assessed using Kolmogorov-Smirnov analysis. Independent T-test (data with normal distribution) or Mann-Whitney U test (if data not normally distributed) will be used to compare these outcomes between the group of membrane sweeping and group of transcervical Foley catheter.
3. Chi-square test will be used to compare:

- a. The requirement of oxytocin augmentation following induction between the group of membrane sweeping and group of transcervical Foley catheter.

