32. Julious SA. Sample size of 12 per group rule of thumb for a pilot study. *Pharm Stat*. 2005;4(4):287-91.

Appendix 1

Study Procedure Flow Chart

Appendix 3

DEPARTMENT OF O&G, SIBU HOSPITAL, SARAWAK

DATA COLLECTION FORM

**MEMBRANE SWEEPING VERSUS TRANSCERVICAL FOLEY CATHETER
FOR INDUCTION OF LABOUR IN WOMEN WITH PREVIOUS
CAESAREAN DELIVERY**

Patient ID :

Name : **Date/time of admission:**

IC Number : **Date/time of discharge :**

MRN :

Age :

Ethnicity : Iban Melanau Bidayuh Malay
 Chinese Indian Other Foreigner

ALLOCATED GROUP: (PLEASE TICK)

MEMBRANE SWEEPING

TRANSCERVICAL FOLEY CATHETER

SECTION A: DEMOGRAPHIC INFORMATION

Gravida / Parity:/..... Gestational age at induction of labour: weeks days

EDD/REDD:

Height (m):

Weight (kg): (at booking) (at delivery)

BMI (kg/m²):

Previous Caesarean section: *(please tick)*

a) Untested scar

If untested scar, any previous vaginal delivery?

Yes

No

b) Tested scar

Indication of induction of labour: *(please tick)*

a) Postdate

b) Fetal growth restriction

c) Hypertension

d) Diabetes

e) Other

Please specify:

SECTION B: INDUCTION OUTCOMES ***Modified Bishop score is used in this study*

Modified Bishop score:

a) At the start of induction

b) When Foley catheter dislodged < 24 hours

a) After 24 hours of induction

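### A vasovagal attack after membrane sweeping triggers mandatory withdrawal, data destruction and replacement, a post-randomisation exclusion written for one arm only

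*Combined protocol and SAP*

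**What the plan says.** Assessment of Safety, item 4, sets out the handling of five adverse events.

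- **Vasovagal attack following sweeping (4.b).** Item 4.b.i stops further sweeping. Item 4.b.ii adds "Affected subject will be withdrawn from the study". Item 4.b.iii then says "No rescue medication is needed as condition is self-limiting", and vital signs and oxygen saturation are monitored for 24 hours.
- **Latex allergy with the Foley catheter (4.a).** "Foley catheter will be removed immediately", followed by rescue medication and 24 hours of monitoring. Her study status is not mentioned.
- **Cervical tear, uterine rupture, maternal sepsis (4.c to 4.e).** Treatment, then follow-up to 42 days after delivery. No withdrawal is listed.

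Selection and Withdrawal of Subjects, item 6.b.ii, states: "The withdrawn subjects data will be destroyed as it will not be used for data analysis". Item 6.c states: "The withdrawn subjects will be replaced with new subjects in order to meet the required sample size". Neither is limited to particular reasons for withdrawal.

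Under Trial Design, items 5.f and 5.h, the allocation envelope is opened once consent is signed, and induction takes place the next morning. The Statistics section defines no analysis population and contains no intention-to-treat statement.

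**The concern.** A randomised comparison is protected by keeping every woman in the group to which she was allocated. Here a woman is removed because of something the allocated procedure did to her, after randomisation and after induction has begun. The rule has no written counterpart in the Foley arm, so the two groups analysed are selected differently.

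The primary outcome is the overall induction to delivery interval, which exists for this woman whether or not sweeping continues. Removing her discards an observable outcome and puts in her place a woman who did not have the reaction. If women who stop sweeping deliver later, this flatters sweeping. If they go to an early Caesarean, their interval is shorter and removal works against sweeping.

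**Working it through.** **Reading the text**

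1. *Does 4.b.ii mean more than stopping the method?* Yes. Item 4.b.i already stops sweeping, so 4.b.ii would be redundant if it meant only that, and its wording refers to the study.
2. *Do the destroy and replace rules apply to her?* Item 6.a lists three withdrawal criteria: request, ineligible enrolment, and spontaneous labour before the procedure. Vasovagal attack is not among them, so the link joins two sections. Items 6.b.ii and 6.c cover withdrawn subjects in general, and nothing exempts her.
3. *Is it always post-randomisation?* Yes. Allocation is known the day before the first sweep.
4. *Is it one-sided?* All three criteria in 6.a are open to both arms. Item 4.b.ii is the only trigger that is both mandated and specific to one arm's method.
5. *Could her outcome still be collected?* Yes. Appendix 3, Section C, records the induction to delivery interval whatever the mode of delivery. The plan already keeps collecting data when a method ends early: Appendix 3, Section B, has an entry headed "When Foley catheter dislodged < 24 hours".

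**Size**

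The plan has no figure to reproduce: it gives no vasovagal rate, standard deviation, target difference or final sample size. The only arm size stated is for the interim: "we will recruit 24 subjects (a sample size of 12 per group) first". Everything else below is an illustration on assumed values.

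*Arm sizes.* The protocol's formula is n = 1 + 2C(s/d)², with alpha 0.05, power 0.8 and 15% dropout. C = (1.960 + 0.842)² = 7.85.

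- d/s = 0.8 (assumed): 1 + 15.7/0.64 = 25.5, so 26; 26/0.85 gives 31 per arm.
- d/s = 0.5 (assumed): 1 + 15.7/0.25 = 63.8, so 64; 64/0.85 gives 76 per arm.

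*Removals.* With assumed rate f per woman and n in the sweeping arm, expected removals are f × n, and the chance of at least one is 1 − (1 − f)ⁿ.

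| f (assumed) | Expected, n = 12 | Expected, n = 31 | Expected, n = 76 | At least one, n = 12 | At least one, n = 76 |
|---|---|---|---|---|---|
| 0.5% | 0.06 | 0.155 | 0.38 | 5.8% | 31.7% |
| 1% | 0.12 | 0.31 | 0.76 | 11.4% | 53.4% |
| 5% | 0.60 | 1.55 | 3.80 | 46.0% | 98.0% |

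*Shift in the sweeping mean.* Let m be the mean of the retained women and m + D the mean of those removed. The mean as randomised is (1 − f)m + f(m + D) = m + fD. The analysed mean is m, so removal changes it by −fD.

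| f (assumed) | D = +24 h (assumed) | D = −12 h (assumed, early Caesarean) |
|---|---|---|
| 0.5% | −0.12 h | +0.06 h |
| 1% | −0.24 h | +0.12 h |
| 5% | −1.2 h | +0.6 h |

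*Interim.* One such woman among 12 moves the sweeping mean by 24/12 = 2 h down, or 12/12 = 1 h up. The interim data also feed the final sample size calculation.

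**The case against.** The strongest reply is that this is one rarely used trigger of a wider rule. The damage comes mainly from items 6.b.ii and 6.c, which govern all withdrawals in both arms. That is true, and the two should be mended together. But revising item 6 alone would leave 4.b.ii in force: she would still be withdrawn, with no stated outcome collection to delivery.

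Second, not everything about her would vanish. Assessment of Safety, item 3.c, names vasovagal attack as reportable, with an initial and a follow-up report. So a safety record should survive, and full destruction sits awkwardly with that duty. The report does not put her interval back into the analysis.

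Third, some contrasts are imperfect, and this stands. The 42-day follow-up is for safety and does not settle how those women are analysed. The form's entry for a dislodged catheter concerns spontaneous expulsion, not stopping for an adverse event. For latex allergy the plan is silent, so the text shows that withdrawal is written for one arm, not that a woman with latex allergy would be kept.

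Fourth, the size is assumed throughout, and 5% has no support in the documents. At 0.5% to 1% the shift is 0.06 to 0.24 h in either direction, against an interval from sweeping to delivery that the background puts at about 4 days in one cited study. This stands, and it limits the weight of the point.

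Last, a retained woman needs a plan for the second day, since Trial Design, item 5.m.ii, continues sweeping and 4.b.i forbids it. This too is fair, and the fix covers it.

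**Conclusion.** The concern holds. Followed as written, the plan creates a post-randomisation exclusion that is caused by the allocated method and mandated in the sweeping arm only, with no analysis rule to undo it. This rests on the natural reading that the general withdrawal rules apply to a woman withdrawn under 4.b.ii.

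The numerical effect is unknown and may well be small. On the assumed inputs it runs from about 0.1 h to about 1 h in the sweeping mean, with uncertain sign. It is most visible at the interim, where a single removal could matter. It should be corrected because the exclusion is unnecessary and easily avoided, not because it is likely by itself to change the trial's conclusion.

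**What to change.** - Delete item 4.b.ii and keep 4.b.i, so that sweeping still stops.
- State that after a vasovagal attack the woman stays in her allocated group, is not replaced, has all outcomes collected to delivery, and is analysed as randomised.
- State the same for latex allergy and any other early removal of the catheter, so that stopping the method is not withdrawal in either arm.
- Add a line on her care if the cervix is unfavourable at 24 hours. Conservative management with reassessment the next day, as Trial Design item 5.m.ii already provides for the Foley arm, or local protocol, would serve.
- If the destroy and replace rules in items 6.b.ii and 6.c are revised, make both changes in the same amendment.
- Optionally, add tick boxes for vasovagal attack and latex allergy to the data collection form, since neither is currently tabulated.

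The cost is one line deleted and a few sentences added. No extra visits, procedures or outcome measurements are needed beyond what is already recorded to delivery.

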- j. In Group 2, transcervical Foley catheter No. 18 F will be inserted under aseptic technique into the endocervical canal surpassed beyond the internal os. The balloon will be inflated with 60 ml of sterile water and the catheter is plastered to patient's thigh with gentle traction. The catheter will be checked for its position and the traction at 6 hours interval. If it were expelled spontaneously, it would not be re-inserted. Otherwise, the catheter will be removed after 24 hours.
- k. Post-induction CTG will be performed at 1 hour after the first membrane sweeping in Group 1 and after transcervical Foley catheter insertion in Group 2.
- l. The uterine contractions, maternal temperature and fetal heart rate (via handheld Doppler device) will be monitored every 4 hours.
- m. After 24 hours, improvement of modified Bishop score will be assessed.
 - i. If the cervix is favourable for amniotomy, amniotomy will be performed followed by augmentation with intravenous oxytocin.

- ii. If the cervix is still unfavourable and amniotomy is impossible, membrane sweeping will be continued for one more day in Group 1 whereas conservative management will be undertaken for one day in Group 2. Suitability for amniotomy will be reassessed on the next day.
 - n. After amniotomy, subsequent intrapartum management will be based on the hospital protocol.
 - o. Oxytocin augmentation will be started when desired contractions are not achieved at 2 hours after amniotomy or labour progress falls below the action line of partogram.
 - p. Our oxytocin infusion regime begins with 2 mU/min. An increment in dosage is made every 30 minutes until desired contractions of 3-4 in 10 minutes lasting 45-60 seconds. The maximum oxytocin dose is 16 mU/min.
 - q. Continuous CTG monitoring will be undertaken throughout the labour process.
 - r. Oxytocin augmentation will not be started or will be withheld when there is non-reassuring fetal heart rate.
 - s. If amniotomy is still impossible after 2 days of IOL, the ward Obstetrician will discuss with women regarding option of Caesarean section.
6. Criteria for suspending or terminating the study:

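### An unspecified normality pretest decides whether the primary outcome, sized on a difference in means, is compared by means or by ranks, and no between-arm difference or confidence interval is planned

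*Combined protocol and SAP*

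**What the plan says.** Assessment of Efficacy, item 1, names the primary outcome: "Overall induction to delivery interval". Under Selection and Withdrawal of Subjects, item 4c, "the final sample size will be calculated based on the study primary outcome of induction to delivery interval", with n = 1 + 2C(s/d)², where s is the standard deviation and d is "the difference to be detected". Alpha is 0.05 and power 0.8. No number is given for s, d or C.

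Statistics, item 2, lists this interval among the numerical variables whose normality "will be assessed using Kolmogorov-Smirnov analysis". The rule that follows is "Independent T-test (data with normal distribution) or Mann-Whitney U test (if data not normally distributed) will be used to compare these outcomes". The section does not say whether the test is corrected for estimating the mean and SD from the data (the Lilliefors version), at what level normality is rejected, or whether the arms are tested separately. Naming SPSS as the software does not settle this.

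The only decision criterion is p < 0.05 (Statistics, item 4). Dummy Table 3 has a column for each arm and one for the p-value. Neither the text nor the tables specify a difference between arms or a confidence interval.

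The schedule in Trial Design, item 5, also matters. "After 24 hours, improvement of modified Bishop score will be assessed"; if amniotomy is not possible then, "Suitability for amniotomy will be reassessed on the next day"; and "If amniotomy is still impossible after 2 days of IOL, the ward Obstetrician will discuss with women regarding option of Caesarean section".

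**The concern.** The plan sizes one quantity and may test another. The formula concerns a difference in mean hours. If the pretest rejects normality, the primary comparison is of ranks, which is not an estimate of that difference. Which of the two is reported stays open until the data are seen. Two analysts following item 2 to the letter could run different primary tests on the same data, in a trial where investigators are not blinded.

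Mann-Whitney is the likelier branch. Amniotomy decisions fall at about 24 and 48 hours, so delivery times should form clusters a day apart rather than a bell shape. This is an inference from the schedule; the documents give no distribution.

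At stake is the interpretability of the main result: how many hours separate the methods, and with what precision.

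**Working it through.** **1. The plan's own figure.** The only stated size is 24 (2 × 12), a pilot rule of thumb, so there is no power calculation to reproduce. With two-sided alpha 0.05 (sidedness assumed) and power 0.8, C = (1.960 + 0.842)² = 7.85. At an assumed d/s of 0.5, n = 1 + 2 × 7.85 × 4 = 63.8, so 64 per arm. At d/s of 0.4, 0.6, 0.8 and 1.0 the formula gives 100, 45, 26 and 17. The ordinary two-means formula, 2C(s/d)², gives 62.8 at d/s = 0.5. The protocol's formula is therefore the two-means formula plus 1, and d is a difference in means.

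**2. Which test the pretest would choose.** Reading assumed: each arm is tested at 5% with estimated mean and SD, and Mann-Whitney is used if either arm rejects. The critical distance is 0.110 (Lilliefors) v 0.167 (uncorrected) at n = 64, and 0.159 v 0.242 at n = 30. All shapes are assumptions. Simulated share of trials sent to Mann-Whitney:

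| Assumed shape | Per arm | Lilliefors | Uncorrected |
|---|---|---|---|
| Normal | 30 or 65 | about 10% | 0% |
| Gamma, shape 4 | 65 | 76% | 6% |
| Lognormal, sigma 0.5 | 30 | 74% | 7% |
| Day-grouped | 30 | 92 to 100% | 8 to 81% |
| Day-grouped | 64 | 100% | 61 to 100% |

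Day-grouped means 24 h plus labour if amniotomy is done at 24 h. Otherwise it is 48 h plus labour (two thirds) or 48 h plus a short gamma delay (one third). Labour averages 8 h with SD 4, 6 or 8, and 0 to 20% labour early.

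**3. Rejection when the means are equal.** When both arms share one distribution, the two-step rule rejects in 4.1 to 5.9% of trials (12 to 100 per arm, four shapes, both versions). With equal means and SDs but different shapes (lognormal, sigma 0.8, v normal):

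| Per arm | t-test | Two-step, Lilliefors | Two-step, uncorrected |
|---|---|---|---|
| 30 | 5.0% | 8.0% | 6.3% |
| 65 | 5.5% | 12.6% | 11.4% |
| 100 | 5.1% | 17.5% | 17.3% |

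**4. Power with day-grouped intervals and the same late tail in both arms**, 64 per arm, Lilliefors version. The three shares are amniotomy at 24 h / at 48 h / neither. For 70/20/10 v 50/25/25, the planned rule rejects in 48% and a mean comparison in 58%. For 60/20/20 v 50/25/25, the figures are 17% and 19%. Across the wider set of day-grouped settings, with baseline score unrelated to the interval, adjusted regression minus the two-step rule ranges from −0.1 to 8.3 points at 64 per arm, and from −0.4 to 6.9 at 30.

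**5. What a mean comparison could cost.** Smooth right-skewed data (gamma, shape 4), equal shapes, 64 per arm, shift set for 80% t-test power; r is the assumed correlation of baseline Bishop score with the interval:

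| r | Adjusted regression | Two-step, Lilliefors | Difference (points) |
|---|---|---|---|
| 0 | 79.1% | 84.9% | −5.8 |
| 0.1 | 78.9% | 84.2% | −5.3 |
| 0.2 | 80.1% | 83.3% | −3.2 |
| 0.3 | 83.1% | 83.0% | +0.1 |
| 0.4 | 85.8% | 82.6% | +3.2 |
| 0.5 | 89.4% | 81.8% | +7.6 |

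**The case against.** The case for leaving the rule alone is a fair one. Choosing the test after a normality check is familiar. When the arms share one distribution, its error rate is close to nominal. With smooth skew and a pure shift, ranks gain power: for gamma data at 65 per arm, Mann-Whitney has 84.5% against 80.3% for the t-test. A rank comparison also answers a sensible question. All of this stands, but it does not supply the quantity the trial is sized on, or say in advance which question will be answered.

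Four stronger readings are tempting and are not supported.

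- *The planned rule would miss most real differences.* This takes an assumed case: 60/20/20 in both arms, with the last 20% delivering at about 54 h with Foley and 100 h with sweeping. The mean difference is 0.20 × 46 = 9.2 h, and the planned rule rejects in 15% against 70% for adjusted regression. But Trial Design 5s applies the same two-day rule to both arms. The Background's delay of up to 8 days cites a trial in low-risk women at term, not women with a scar on this schedule. With tails at 54 v 60 h the planned rule does slightly better (12% v 9%).
- *The rank test would favour the wrong arm.* With Foley 50/40/10 v sweeping 70/15/15 and the same 54 and 100 h tails, the mean is 2.0 h longer with sweeping, yet ranks favour sweeping significantly in 22%. This needs the same sweeping-only tail. Both cases are extreme illustrations.
- *The plan inflates type I error in general.* It does not when distributions are identical. The excess in step 3 arises when shapes differ, and then only as a test of equal means.
- *Readers would get a p-value and nothing else.* Table 3 has a column for each arm. What is missing is the difference and its precision.

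**Conclusion.** The point holds and should be corrected. Its main consequence is an undefined primary effect measure with no planned precision. That follows from the text alone and needs no simulation.

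Selection of Mann-Whitney is probable rather than certain. It rests on the day-grouping inference and is weakest with the uncorrected test at small sizes. The 8 to 18% rejection under equal means applies to the Lilliefors version at 30 to 100 per arm and to one assumed pair of shapes. The power difference with a common late tail is modest, about 0 to 10 points in favour of means at 64 per arm. With smooth skew it can reverse. The 64 per arm is itself illustrative, since the documents give no s, d or final n.

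**What to change.** For the primary outcome only:

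- Delete the normality pretest.
- Pre-specify linear regression of the induction to delivery interval in hours on allocated arm and baseline modified Bishop score, with robust (HC3) standard errors and no other covariate. Report the adjusted mean difference with its 95% CI.
- Use the score assessed for eligibility, recorded before the envelope is opened. The form's present item is taken at the start of induction, which is the morning after an unblinded allocation. If no pre-allocation score is recorded, use an unadjusted Welch comparison with its CI. That alone cures the main fault; the documents give no correlation that would make adjustment essential.
- Add a column for the difference and CI to dummy Table 3.
- Keep Mann-Whitney as a sensitivity analysis that does not decide the result.

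The cost is a few lines in Statistics, one table column and one line on the data collection form. A score of 6 or less is already an inclusion criterion, so no extra examination is needed. The sample size formula can stay, because it already sizes a difference in means. The plan should state the downside: about 3 to 6 points of power may be lost against the present rule if the data are smoothly skewed and the baseline correlation is weak.
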